10.2.2 Secondary efficacy analyses

10.2.2.1 Patient Global Impression of Change (PGIC)

This endpoint will follow the same method of analysis as for the primary endpoint (see 10.2.1.1), but no LME will be fitted. No baseline PGIC term will be fitted in the MMRM since this is not applicable at baseline.

Additionally, PGIC will be summarized using counts and percentages of patients in each of the 7 levels and will be compared between treatment groups using the Wilcoxon rank-sum test, stratified by the FSHD repeat number category.

The number and percentage of patients reporting improvement, i.e., PGIC of 3 or less, and those without reporting improvement, i.e., PGIC of 4 or more, will also be presented for each treatment group. A patient with a missing PGIC value will be considered as not reporting improvement. The proportion of patients reporting improvement at Week 48 will be compared between treatment groups using the Cochran-Mantel-Haenszel test stratified by FSHD repeat number category.

Similar analysis will be performed for the number and percentage of patients without reporting worsening, i.e., PGIC of 4 or less, and those reporting worsening, i.e., PGIC of 5 or more, with between-treatment comparison using the Cochran-Mantel-Haenszel test stratified by FSHD repeat number category. A patient with a missing PGIC value will be considered as reporting worsening.

A sensitivity analysis of this endpoint will be carried out using the MMRM based on the on-treatment measurements up to 2 days (inclusive) after the last dose of study drug for patients in the FAS. Another sensitivity analysis will adjust for correct FSHD repeat number category (see 10.2.1.2).

The analysis will be repeated for each subgroup listed in Section 8.5.

PGIC scores will be presented by patient in a listing, by FSHD type and treatment group.

10.2.2.2 Change from baseline in whole body (WB) longitudinal composite MFI (B muscles)

This endpoint will follow the same method of analysis as for the primary endpoint (see 10.2.1.1) using an MMRM. The primary analysis of this endpoint will be based on the MMRM. An LME will also be fitted as defined in 10.2.1.1, where the dependent variable is absolute WB composite MFI, measured at baseline and each post-baseline visit.

Additionally, this endpoint will be analyzed using the Wilcoxon rank-sum test, stratified by the FSHD repeat number category (see 8.2). The Hodges-Lehmann estimate of the associated treatment

REACH TRIAL

difference and asymptotic nonparametric 95% confidence interval will be computed. Median change from baseline will be plotted by treatment group.

A sensitivity analysis of this endpoint will be carried out based on the on-treatment measurements up to 2 days (inclusive) after the last dose of study drug for patients in the FAS. Another sensitivity analysis will adjust for correct FSHD repeat number category (see 10.2.1.2).

The analysis will be repeated for each subgroup listed in Section 8.5.

All WB longitudinal composite endpoint data and cross-sectional composite data (MFI/MFF/LMV) will be presented by patient in a listing, by FSHD type and treatment group.

10.2.2.3 Relative change from baseline in average shoulder abductor strength by handheld quantitative dynamometry at Week 48

This endpoint will be analyzed using the Wilcoxon rank-sum test, stratified by the randomization stratification factor (see 8.2). The Hodges-Lehmann estimate of the associated treatment difference and asymptotic nonparametric 95% confidence interval will be computed. Median relative change from baseline will be plotted by treatment group.

A sensitivity analysis of this endpoint will be carried out based on the on-treatment measurements up to 2 days (inclusive) after the last dose of study drug for patients in the FAS. Another sensitivity analysis will adjust for correct FSHD repeat number category (see 10.2.1.2).

The analysis will be repeated for each subgroup listed in Section 8.5.

All dynamometry data will be presented by patient in a listing, by FSHD type and treatment group.

[figure not shown]

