2.4.2 Multiple testing strategy

To control the overall type I error rate, the primary endpoint and secondary efficacy endpoints will be tested in sequence as follows:

1. The primary endpoint will be tested at 2-sided significance level $\alpha=0.05$.
2. If a statistically significant result is obtained for the primary endpoint (test 1), change from baseline in WB longitudinal composite MFI in B muscles at Week 48 and relative change from baseline in average shoulder abductor strength by hand-held quantitative dynamometry at Week 48 will be tested using the Bonferroni procedure, i.e., each will be tested at 2-sided $\alpha = 0.025$ (test 2).
 - If both tests are significant, a statistically significant result is obtained from test 2. The remaining significance level from test 2 = 0.05.
 - If only one of the 2 tests is significant, a statistically significant result is obtained from test 2. The remaining significance level from test 2 = 0.025.
 - If neither test is significant, a statistically significant result is not obtained from test 2.
3. If a statistically significant result is obtained from test 2, PGIC at Week 48 will be tested at the remaining significance level from test 2 (test 3).
4. If a statistically significant result is obtained from test 3, change from baseline in Neuro-QoL-UE at Week 48 will be tested at the remaining significance level from test 3, which is equal to the remaining significance level from test 2.

In recognition of the complexities of this rare disease and the novelty of this research field, in case the result of the primary analysis (MMRM) of the primary endpoint is on the boundary of statistical significance, but at least one of the following is true:

- results from most sensitivity analyses are nominally significant,
- result of PGIC at Week 48 is nominally significant,
- result of Change from baseline in WB longitudinal composite MFI in B muscles at Week 48 is nominally significant,

AND

- results from most of the remaining secondary and exploratory efficacy endpoints are directionally favorable to losmapimod,

the totality of evidence will be utilized to support the decision making.

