5. SAMPLE SIZE CONSIDERATIONS

The target population for this clinical trial is patients with FSHD1 and FSHD2. The clinical trial will reflect the current epidemiologic information about FSHD, with patients with FSHD1 making up approximately 95% of the study population and the other 5% being people living with FSHD2.

Assuming the within-group standard deviation (SD) of change is 0.08, a sample size of 210 patients with FSHD1 (105 patients per group) will be needed to provide at least 95% power with a 2-sided t-test at 0.05 significance level to detect a difference of 0.05 between losmapimod and placebo for the primary endpoint. An additional approximately 20 patients with FSHD2 will be recruited. The primary analysis will include patients with FSHD1 and FSHD2. Premature withdrawal and missing data are discussed in 9.1.

For the secondary efficacy endpoints of change from baseline in WB longitudinal composite MFI of B Muscles and PGIC at Week 48, assuming the within-group SDs are 0.72 and 1.0 respectively, a sample size of 210 patients with FSHD1 will provide at least 95% power with a 2-sided t-test at 0.025 significance level to detect a difference of 0.5 and 0.6 respectively between losmapimod and placebo.

For the secondary efficacy endpoint of relative change from baseline in average shoulder abductor strength at Week 48, assuming the within-group SD is 46, a sample size of 210 patients with FSHD1 will provide at least 75% power with a 2-sided Wilcoxon rank-sum test at 0.025 significance level to detect a difference of 20.2 between losmapimod and placebo.

In the above calculations, the assumed treatment differences and SDs are based on results from an ongoing Phase 2 study, Study FIS-002-2019 (ReDUX4). It is also assumed that 10% of the study population has missing Week 48 data. All power calculations were performed using the POWER Procedure of SAS[®] Version 9.4.

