8.2 STRATA AND COVARIATES

Patients will be randomly assigned at the baseline visit (Day 1) to receive losmapimod (active drug) or placebo using a 1:1 allocation ratio. Randomization will be stratified to ensure that treatment allocation is balanced across 3 strata based on FSHD repeat number category and FSHD type:

- FSHD 1, repeat numbers 1-3
- FSHD 1, repeat numbers 4-9
- FSHD 2

Inferential models will be adjusted for the above 3-level FSHD repeat number category (except subgroup analyses by FSHD Repeat Number Category). If the stratification category used at randomization is different from the correct category, the stratification category used in analyses will be the category used at randomization for the primary analyses of the primary endpoint and alpha-protected secondary endpoints (see 2.4.2), while the correct category will be applied in the sensitivity analyses of the primary endpoint and alpha-protected secondary endpoints, and the correct category will be applied in all other efficacy analyses. If the number of patients with non-missing data in any level of the FSHD repeat number category < 5 in either treatment group in any inferential analysis, the data from that level in both treatment groups will not be included in that inferential analysis. If such a situation occurs in at least 2 of the 3 levels, the inferential analysis will be performed on data from all patients without adjusting for the 3-level FSHD repeat number category. All inferential models will include a fixed effect for region: North America / Europe (except subgroup analyses by region). If the number of patients with non-missing data in either region < 5 in either treatment group in any inferential analysis, the inferential analysis will be performed on data from all patients without adjusting for region.

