9.3.3.2 Secondary endpoints

PGIC at Week 48

PGIC is a single-item rating scale. Patients will be asked to rate their overall status relative to baseline: 1 = Very much improved, 2 = Much improved, 3 = Minimally improved, 4 = No change, 5 = Minimally worse, 6 = Much worse, 7 = Very much worse. The PGIC is measured at weeks 4, 12, 24, 36 and 48. Missing values are treated as missing.

Change from baseline in whole-body (WB) longitudinal composite muscle fat infiltration (MFI) (B muscles) at Week 48

This endpoint is derived for B-muscles as described in 9.3.1.3, where Y=MFI.

Relative change from baseline in average shoulder abductor strength by hand-held quantitative dynamometry at Week 48

Shoulder abductor strength is measured three times on each arm at baseline, weeks 4, 12, 24, 36, and 48, and a mean value is recorded in the EDC. At each timepoint, the average mean for the two arms will be derived, and a relative change of this average from baseline will be derived as specified in 9.2. above.

Missing values will be treated as missing.

[figure not shown]
Change from baseline in Neuro-QoL-UE Function at Week 48

[figure not shown]
The Neuro-QoL-UE is a 20-item questionnaire, from which a single scale is derived. It is measured at baseline and at weeks 4, 12, 24, 36 and 48. The Neuro-QoL-UE measures ability across fine motor and activities of daily living involving digital, manual, and reach-related function and self-care. Responses are divided into 5 ordinal levels (1 = unable to do, 2 = with much difficulty, 3 = with some difficulty, 4 = with a little difficulty, 5 = without any difficulty). The endpoint is derived as:

[figure not shown]
$$20 \times (\text{Sum scores from all items answered}) / (\text{Number of items answered})$$

[figure not shown]
The Neuro-QoL-UE will be recorded as missing if fewer than 10 items are answered. The score ranges from 20-100, with higher scores reflecting better upper extremity fine motor function.

Change from baseline is derived as specified in 9.2. above.

[figure not shown]
Change and relative change from baseline in muscle strength by hand-held quantitative dynamometry

There are eight dynamometry outcomes measured at baseline and at weeks 4, 12, 24, 36 and 48. They relate to 4 assessment areas:

- [1] Average dominant shoulder abductor strength (kg)
- [2] Average non-dominant shoulder abductor strength (kg)
- [3] Average dominant hand grip strength (kg)
- [4] Average non-dominant hand grip strength (kg)

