10.2 EFFICACY ANALYSES

Efficacy analyses are based on the FAS. The primary and secondary efficacy analyses will also be split by subgroup of the FAS.

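### The alpha-protected shoulder-strength test has no method for missing Week 48 values, and is biased if the link between strength and dropout differs by arm or a shared link meets clearly unequal dropout rates

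*SAP*

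**What the plan says.** - **Status.** SAP 2.4.2 places this endpoint in the second step of the testing sequence, paired with MFI: "relative change from baseline in average shoulder abductor strength by hand-held quantitative dynamometry at Week 48 will be tested using the Bonferroni procedure", at two-sided 0.025 each. Success on either one releases alpha to PGIC and then to Neuro-QoL-UE.
- **Analysis.** SAP 10.2.2.3: "This endpoint will be analyzed using the Wilcoxon rank-sum test, stratified by the randomization stratification factor", applied to relative change at Week 48.
- **Missing data.** SAP 9.3.3.2, for this endpoint: "Missing values will be treated as missing". SAP 10.2 says "Efficacy analyses are based on the FAS", but no rule gives a score to an FAS patient without a Week 48 value.
- **Who counts as observed.** Under SAP 9.5.1 the Week 48 window runs from Day 295 to the earlier of Day 357 or the first open-label dose. Unscheduled and early-termination values inside it count. Under SAP 9.3.1.1 one measured arm is enough.
- **Sensitivity analyses.** There are two: on-treatment values only, which can only remove data, and the correct stratum. The imputation analyses in SAP 10.2.1.2 are for RSA only.
- **Other confirmatory endpoints.** RSA, MFI, PGIC and Neuro-QoL-UE are analysed with an MMRM, which uses a patient's earlier visits.
- **Power.** SAP 5: "assuming the within-group SD is 46, a sample size of 210 patients with FSHD1" gives "at least 75% power with a 2-sided Wilcoxon rank-sum test at 0.025 significance level to detect a difference of 20.2". The same section adds: "It is also assumed that 10% of the study population has missing Week 48 data".

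**The concern.** A rank-sum test at one visit cannot use earlier visits. A patient measured through Week 36 who then leaves contributes nothing to this test, but does contribute to the MMRM endpoints. If the reasons for leaving are tied to strength differently in the two arms, the patients left at Week 48 are no longer comparable.

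- If weaker losmapimod patients are lost, the drug looks better than it is and false positives follow. In this sequence they would also release alpha to PGIC and Neuro-QoL-UE.
- If weaker placebo patients are lost, a real effect is hidden.

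The plan itself treats outcome-related missingness as possible. SAP 9.3.3.1 scores an arm that cannot be tested for weakness as 0 for reachable workspace, and SAP 10.2.1.2 separates RSA missingness by reason for discontinuation. Dynamometry has neither rule.

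**Working it through.** **1. Reproduce the stated power.** Inputs from SAP 5 and 8.2: 210 FSHD1 patients, allocated "using a 1:1 allocation ratio", so 105 per arm; 10% missing, so 105 × 0.9 = 94.5 per arm; SD 46; difference 20.2; two-sided 0.025, critical value 2.24. Wilcoxon efficiency under normality is 3/π = 0.955.

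- Effective n = 94.5 × 0.955 = 90.2 per arm
- SE = 46 × √(2/90.2) = 6.85
- Power = Φ(20.2/6.85 − 2.24) = Φ(2.95 − 2.24) = Φ(0.71) = 76%

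This matches the plan. A stratified simulation at 94 to 95 per arm gives 75.6%. With no missing data the formula gives 80.7%, so the 10% loss is already in the stated figure.

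**2. When the test keeps its size.** Under the null, suppose a patient's chance of being observed depends on strength in the same way and at the same rate in both arms. The observed patients in each arm then come from the same distribution, and the rank test is valid. It is also valid when dropout is unrelated to strength, whatever the rates. Simulation with 105 per arm, Week 36/48 correlation 0.75 and dropout logistic in the Week 36 value (6,000 null trials) agrees:

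- random dropout: error 2.4%
- shared link, 10% in each arm: 2.8% (slope 1 per SD) and 2.4% (slope 2)
- shared link, slope 1, 12% versus 8%: 2.8%

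Power at 20.2 is 75% with random dropout, and 74% and 69% with the shared link at equal rates.

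**3. When it does not.** The documents do not give the strength–dropout link, so it is varied.

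*Moderate link, one arm only.* In the same setting, slope 1 gives error of 3.6% to 4.5%. A stronger logistic link (1,500 trials per setting) gives about 6.5%. With that stronger link in placebo only, the mean estimate is 16.0 instead of 20.2 and power is 56%, against 77% with random dropout. In losmapimod only, the estimate is 24.4.

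*Strong link.* Stratified test, 115 per arm (FSHD2 included), assumed strata of 21/84/10 per arm, correlation 0.7; where weaker patients leave, those with the lowest Week 36 change are the ones lost (3,000 null and 1,500 alternative trials). Imputation uses arm and the Week 36 change, followed by the same test and pooling.

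| Dropout, losmapimod/placebo | Observed-case error | Observed-case power | Imputed error | Imputed power |
|---|---|---|---|---|
| 10%/10%, unrelated | 2.5% | 80% | 2.4% | 82% |
| 15%/5%, unrelated | 2.2% | 81% | 2.2% | 83% |
| 15%/5%, weaker leave in both | 8.1% | 95% | 2.8% | 81% |
| 5%/15%, weaker leave in both | 8.9% | 58% | 1.9% | 82% |
| 10%/10%, weaker leave losmapimod only | 9.3% | 97% | 2.4% | 81% |
| 10%/10%, weaker leave placebo only | 9.6% | 47% | 2.4% | 81% |

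Nearly all the excess error favours losmapimod in rows 3 and 5, and placebo in rows 4 and 6.

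*Weak link.* With correlation 0.3 between dropout tendency and outcome, the last four patterns give error of 3.8% to 4.0%. Power is 66% to 69% in the two patterns that lose weaker placebo patients. The same runs at 0.7 give error of 8% to 11%.

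Monte Carlo standard errors for the table are about √(0.025 × 0.975/3,000) = 0.3 points near 2.5% error, 0.5 points near 9%, and 1.0 to 1.3 points for power (except rows above 90%, where it is smaller). One run that removed a fixed tenth of both arms, the weaker patients in each, gave 3.3%. Trimming a fixed count makes the arms vary more than independent dropout does; the logistic runs in step 2 are the fairer check of that case.

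**The case against.** Several points on the other side stand.

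- **The test is not invalid whenever dropout relates to strength.** A reader might infer this, but step 2 shows that a shared relation at equal rates does no harm to the error rate.
- **Unequal dropout alone is not the problem.** At 15% versus 5% unrelated to strength, error is 2.2%.
- **The plan has not overlooked the 10%.** A reader might think the 75% power ignores it; SAP 5 includes it and step 1 confirms this.
- **Not every early leaver is lost.** Patients who stop treatment are encouraged to stay for assessments, off-treatment values count, and any value from Day 295 is used. The early-termination visit helps less than it seems: under SAP Appendix B, dynamometry is done there only if at least 12 weeks have passed since the last visit, and a value before Day 295 falls in an earlier window.
- **The largest figures need a strong, one-sided pattern.** Nothing in the documents predicts it. Tablets are indistinguishable, and protocol 5.6.1 expects no tolerability difference that would unblind.
- **The good result for imputation is partly built in.** The data were normal and dropout depended on the variable used to impute. Real relative change is bounded at −100% and may be skewed.
- **There is a supportive analysis.** SAP 10.2.3.11 fits an MMRM to absolute change in the same strength measure. It is exploratory and is not the tested quantity.
- **The endpoint is gated.** It is tested only after the primary endpoint succeeds, and the Wilcoxon test follows protocol 9.1.6.4.

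These points limit the size of the concern. They do not supply a missing-data method, or a missing-data sensitivity analysis, for a test that passes alpha onward.

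**Conclusion.** The point holds in conditional form. The confirmatory analysis uses observed Week 48 values only, and nothing prespecified for this endpoint tests how far the result depends on the patients left out. Harm requires a relation between strength and dropout that differs by arm, or a shared one combined with clearly unequal rates. Over assumed weak to strong links, two-sided error is about 3.6% to 10% instead of 2.5% (one run reached 11%), and power is about 47% to 69% when weaker placebo patients are lost. These figures rest on assumed correlations, strata and dropout mechanisms. They are a range of what could happen, not a forecast for this trial. The change should be made, because the data needed are already collected.

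**What to change.** In SAP 10.2.2.3, keep the stratified Wilcoxon test and add a missing-data method:

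1. Multiply impute missing Week 48 strength within arm, from stratum, baseline and the Week 4 to 36 strength values. Use predictive mean matching or a log-strength scale, because relative change is bounded and may be skewed.
2. Derive relative change, apply the stratified test to each of the m completed sets, and pool the standardised statistics: mean z divided by √(1 + (1 + 1/m) × B), where B is the variance of z between imputations.
3. Report the observed-case Wilcoxon test beside it.

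At a minimum, leave the observed-case test primary and prespecify the imputed test as a sensitivity analysis. A tipping-point shift of the imputed values would cover departures from missing at random.

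Ranking every missing patient worst is not a neutral substitute. With 15%/5% dropout unrelated to strength, it gave 13% error and 13% power.

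The cost is SAP wording and a little programming, with no new data. The downside is reliance on missing at random and on an imputation model. SAP 9.1 already assumes missing at random for the primary endpoint; the imputation model is an added assumption.

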10.2.2.4 Change from baseline in Neuro-QoL-UE

This endpoint will follow the same method of analysis as for the primary endpoint (see 10.2.1.1) using an MMRM. The primary analysis of this endpoint will be based on the MMRM. An LME will also be fitted as defined in 10.2.1.1, where the dependent variable is absolute Neuro-QoL-UE, measured at baseline and each post-baseline visit.

A sensitivity analysis of this endpoint will be carried out based on the on-treatment measurements up to 2 days (inclusive) after the last dose of study drug for patients in the FAS. Another sensitivity analysis will adjust for correct FSHD repeat number category (see 10.2.1.2).

The analysis will be repeated for each subgroup listed in Section 8.5.

[figure not shown]
Neuro-QoL-UE scores will be presented by patient in a listing, by FSHD type and treatment group.

[figure not shown]

[figure not shown]
10.2.3.4 Change from baseline in Neuro-QoL individual items

Each of the 20 items of the Neuro-QoL questionnaire will be analyzed as for the primary endpoint (see 10.2.1.1) using an MMRM, but no LME will be fitted.

Neuro-QoL-UE item scores will be presented by patient in a listing, by FSHD type and treatment group.

[figure not shown]

10.2.3.11 Changes from baseline in muscle strength by hand-held dynamometry

A separate analysis will be carried out for each of the 11 dynamometry measures listed in 9.3.3.3 above, expressed as (a) a change from baseline, and (b) a relative change from baseline. Changes from baseline will follow the same method of analysis as for the primary endpoint (see 10.2.1.1). Relative changes from baseline will follow the same method of analysis as for the secondary endpoint of relative change from baseline in average shoulder abductor strength (see 10.2.2.3). All 22 measures modelled will be presented by patient in a listing, by FSHD type and treatment group.

